**Table 6: Plasma Pharmacokinetic Parameters**

Abbreviation	Parameter Definition
AUC 0-∞	For Week 0/Day 1 only, area under the drug concentration-time curve from time zero to infinity, calculated using the linear trapezoidal rule for increasing concentrations and the logarithmic rule for decreasing concentrations as $AUC_{0-tlast} + C_t / \lambda_z$ .
%AUC extrap	For Week 0/Day 1 only, percentage of AUC that is due to extrapolation from the last measurable concentration to infinity
AUC 0-t	For Week 0/Day 1 only, area under the plasma concentration curve over from time 0 to time t, i.e. from 0 to 24 hours, calculated using the linear trapezoidal rule for increasing concentrations and the logarithmic rule for decreasing concentrations.
AUC 0-8hr	For Week 0/Day 1 and Week 6, area under the plasma concentration curve over from time 0 to 8 hours, calculated using the linear trapezoidal rule for increasing concentrations and the logarithmic rule for decreasing concentrations.
AUC tau	For Week 6 and Week 12, area under the plasma concentration curve over a dosing interval, i.e. from 0 to 24 hours, calculated using the linear trapezoidal rule for increasing concentrations and the logarithmic rule for decreasing concentrations.
C max	Maximum observed plasma concentration, obtained directly from the plasma concentration-time profiles within the sampling interval, i.e. calculated for each intensive sampling visit separately (Week 0/Day 1, Week 6, Week 12). In the case where multiple peaks are of equal magnitude, the earliest peak concentration will be reported as C max .
C min	Minimum observed plasma concentration, obtained directly from the plasma concentration-time profiles at steady state, within the sampling interval, i.e. calculated for each intensive sampling visit separately (Week 6 Week 12). In the case where multiple minimums are of equal magnitude, the latest minimum concentration will be reported as C min .

Abbreviation	Parameter Definition
T max	Time of the maximum observed plasma concentration, obtained directly from the plasma concentration-time profiles within the sampling interval, i.e. calculated for each intensive sampling visit separately (Week 0/Day 1, Week 6, Week 12). In the case where multiple peaks are of equal magnitude, the time of the earliest peak will be reported as the t max .
T min	Time of the minimum observed plasma concentration, obtained directly from the plasma concentration-time profiles at steady state, within the sampling interval, i.e. calculated for each intensive sampling visit separately (Week 6 Week 12). In the case where multiple minimum are of equal magnitude, the time of the latest minimum will be reported as T min .
T last	Time of the last quantifiable plasma concentration, obtained directly from the plasma concentration-time profiles within the sampling interval, i.e. calculated for each intensive sampling visit separately (Week 0/Day 1, Week 6, Week 12).
t 1/2	Apparent plasma terminal elimination half-life, calculated as $\ln(2) / \lambda_z$ .
CL/F	Apparent total plasma clearance calculated as Dose / AUC 0-∞ for Week 0/Day 1
CL ss /F	Apparent total plasma clearance at steady state, calculated as Dose / AUC τau for Week 6 and Week 12.
V z /F	Apparent volume of distribution, calculated as Dose / ( $\lambda_z * AUC_{0-∞}$ ) for Week 0/Day 1
V ss /F	Apparent volume of distribution, calculated as Dose / ( $\lambda_z * AUC_{τau}$ ) for Week 6 and Week 12.
RA AUCτau	Observed accumulation ratio based on AUC τau calculated as AUC τau (Week 6 and Week 12) / AUC 0-24hr (Day 1).
RA Cmax	Observed accumulation ratio based on C max , calculated as C max (Week 6 and Week 12) / C max (Day 1).
LR	Linearity ratio calculated as AUC τau (Week 6 and Week 12) / AUC 0-∞ (Day 1)
C avg	Average observed drug concentration at steady state (Week 6 and Week 12 only)
C 24	For Week 0/Day 1, observed drug concentration at the end of the dosing interval, e.g. from 0 to 24 hours
C τau	Observed drug concentration at the end of the dosing interval, e.g. from 0 to 24 hours (Week 6 and Week 12 only)
λ z	Apparent terminal rate constant (listed only)

In addition, the metabolite-to-parent ratios will be calculated for AUCτau, Cτau, and Cmax. Metabolite-to-parent ratios will be corrected for molecular weight differences by multiplying the ratio by a correction factor. The correction factor for TRN-001021 ratios is 1.05 and the correction factor for TRN-001744 ratios is 1.42.

Additional PK parameters may be determined where appropriate.

#### **8.7.4.1. Pharmacokinetic Parameter Data Handling**

#### **8.7.4.2. Calculation of AUC**

AUCs will be calculated using linear up / log down trapezoidal rule. For any partial AUC determination (i.e., AUC over a dosing interval), nominal time will generally be used for the end of the interval. Actual times for partial AUC intervals may be used at the discretion of the pharmacokineticist.

The minimum requirement for the calculation of AUC will be the inclusion of at least three consecutive plasma concentrations above the LLOQ, with at least one of these concentrations following  $C_{\max}$ .

#### **8.7.4.3. Criteria for Calculation and Goodness of Fit**

Values for  $\lambda_z$ ,  $t_{1/2}$ ,  $AUC_{0-\infty}$ ,  $CL/F$  and  $CL_{ss}/F$ ,  $V_z/F$  and  $V_{ss}/F$ , and LR will only be reported if the following criteria for the terminal elimination phases (log-linear phase) for the concentration-time data are met:

- A minimum of 3 measurable concentration-time-points during the log-linear portion of the terminal elimination phase (after  $T_{\max}$ ), excluding  $C_{\max}$ .
- $r^2_{\text{adj}} \geq 0.80$  for the regression of the log-concentration time data during the terminal elimination phase.
- Negative slope for log regression fit.

$AUC_{0-\infty}$  values where the percentage extrapolation is greater than 30% will be reported and flagged but excluded from descriptive statistics. Parameters affected by  $AUC_{0-\infty}$  such as  $t_{1/2}$ ,  $CL/F$ ,  $V_z/F$ , and LR will be handled the same way as  $AUC_{0-\infty}$ .

Additional analyses will be performed as deemed necessary upon review of the data.

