Plasma exposures to TERN-201 were greater than dose proportional. TERN-201 was rapidly cleared from plasma. Steady state was achieved in the highest dose group (10 mg) after Day 7 of dosing. The half-life of TERN-201 increased with dose, suggesting saturable, target-mediated clearance.

Single and multiple doses of TERN-201 significantly suppressed plasma total amine oxidase activity at all doses studied. Using an exploratory assay to assess the effect of TERN-201 on VAP-1/SSAO-specific amine oxidase activity in the plasma, near complete inhibition (>80% with 1 mg, > 90% with 10 mg) was observed after only a single dose on Day 1 (achieved within 4 hours after dosing) with sustained suppression over the dosing period in MAD cohorts. Dose-dependent increases in methylamine, an endogenous substrate of VAP-1/SSAO predicted to increase upon VAP-1/SSAO inhibition, were observed after the first dose of TERN-201 and continued to increase in a dose-dependent manner after multiple doses of TERN-201.

Based on the exploratory assessment on plasma PK of two TERN-201 metabolites, TRN-001021 and TRN-001744, the percentages of either metabolite AUC relative to the total TERN-201-related plasma AUC (sum of TERN-201, TRN-001021, and TRN-001744) were calculated. Median TRN-001021 AUC was <10% and 13.7% of the total plasma AUC associated with TERN-201 in the 4 mg and 10 mg groups, respectively. Median TRN-001744 AUC was 11.5% and <10% of the total plasma AUC associated with TERN-201 in the 4 mg and 10 mg groups, respectively.

Additional details on Study TERN201-US-A101 are available in the Investigator's Brochure.

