### **3. SAMPLE SIZE JUSTIFICATION**

The sample size is based on clinical feasibility and adequate size to characterize safety in the study population, without consideration for statistical power.

Patients who are randomized but do not receive study drug for any reason may be replaced. Patients who discontinue treatment early for reasons other than safety (e.g. withdrawal of consent, lost to follow-up, patient relocated) may also be replaced.

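### SAP 8.7.4.3 contradicts Table 6 twice: CLss/F is withheld on a terminal-slope test it does not use, and Day 1 t1/2 leaves the summaries on an AUC0-inf rule it does not depend on

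*SAP*

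**What the plan says.** Table 6 of the SAP gives CLss/F as "Apparent total plasma clearance at steady state, calculated as Dose / AUC" with subscript tau, for Weeks 6 and 12. It describes AUCtau as "For Week 6 and Week 12, area under the plasma concentration curve over a dosing interval, i.e. from 0 to 24 hours". The validity rule for an AUC is in section 8.7.4.2: "at least three consecutive plasma concentrations above the LLOQ", at least one of them later than Cmax. Table 6 gives t1/2 as ln(2)/lambda-z. AUC0-inf and its extrapolated percentage are defined for Week 0/Day 1 only.

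Section 8.7.4.3 then sets two restrictions.

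- Lambda-z, t1/2, AUC0-inf, CL/F, CLss/F, Vz/F, Vss/F and LR "will only be reported if the following criteria for the terminal elimination phases (log-linear phase) for the concentration-time data are met". The criteria are "A minimum of 3 measurable concentration-time-points during the log-linear portion of the terminal elimination phase" (after Tmax and not counting Cmax), adjusted r-squared of at least 0.80, and a negative slope. AUCtau is not on this list.
- For AUC0-inf, "values where the percentage extrapolation is greater than 30% will be reported and flagged but excluded from descriptive statistics". The same handling is extended to t1/2, CL/F, Vz/F and LR, on the ground that AUC0-inf affects them.

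Protocol 2.2.2 reports from the first-in-human study: "The half-life of TERN-201 increased with dose, suggesting saturable, target-mediated clearance". The same paragraph says that the drug left plasma quickly. It gives no half-life in hours.

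**The concern.** Each restriction applies a test to a parameter that does not contain the tested quantity. For one patient at one visit, the SAP can report AUCtau and withhold Dose/AUCtau. Section 8.7.5 sets uncalculated values to missing, so the two summaries can rest on different patients even though, at a fixed dose, each determines the other.

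For t1/2 the selection has a direction. With a given last sample and a single decay phase, the extrapolated share rises with half-life, so the rule trims the upper end of the Day 1 distribution. If half-life rises with dose, the trimming falls more heavily on the higher doses and could mask that trend. TERN-201 PK parameters are a secondary endpoint, and intensive sampling covers about 8 active patients in Part 1 and about 6 per dose in Part 2.

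**Working it through.** The plan has no figure to reproduce here; its sample size was set "without consideration for statistical power". The check is first of definitions, then of size.

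**Definitions.** Of the eight parameters on the slope-criteria list, lambda-z, t1/2, AUC0-inf, CL/F, Vz/F, Vss/F and LR all contain lambda-z directly or through AUC0-inf. CLss/F alone does not. Of the parameters tied to the 30% rule, CL/F, Vz/F and LR contain AUC0-inf. The half-life alone does not.

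**Visits affected.** The extrapolated percentage exists on Day 1 only, so the 30% rule cannot act on Week 6 or Week 12 half-lives. Day 1 and Week 6 are both sampled to 24 h; Week 12 is sampled to 72 h.

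**Where the cut falls.** Under mono-exponential decay the extrapolated share is exp(-ln2 × Tlast / t1/2). Setting it to 0.30 gives t1/2 = Tlast × 0.693 / 1.204.

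- Tlast = 24 h: 24 × 0.693 / 1.204 = 13.8 h.
- Tlast = 8 h: 8 × 0.693 / 1.204 = 4.6 h.

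The second case can occur because no sample lies between 8 and 24 h, and SAP 8.7.1 sets unquantifiable values after the last quantifiable one to missing. With first-order absorption (ka 0.7 to 4 per hour, assumed) the cuts are 13.0 to 13.7 h and 3.7 to 4.5 h.

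**Size by simulation.** There were 4,000 profiles per row on the protocol's sampling times, with linear-up/log-down AUC and the SAP criteria. The following are assumptions, not from the documents: a one-compartment oral model, half-life CV 40%, median ka 1.5 per hour, residual error 15% or 30%, all samples quantifiable.

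| Median t1/2 (h) | Day 1 t1/2 left out, 15% / 30% error | Geometric mean t1/2, all → kept (15% error) | Week 6 CLss/F withheld, 15% / 30% error |
|---|---|---|---|
| 3 | 0% / 0% | 3.0 → 3.0 | 0.3% / 2% |
| 6 | 2% / 2% | 5.9 → 5.8 | 3% / 15% |
| 10 | 20% / 15% | 9.7 → 8.4 | 13% / 35% |
| 14 | 46% / 31% | 13.2 → 9.7 | 24% / 50% |
| 20 | 74% / 59% | 18.1 → 10.8 | 37% / 65% |

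The half-life percentages are of values that already passed the slope criteria. The CLss/F percentages are of profiles with an evaluable AUCtau. The withheld CLss/F values were close to the truth (geometric mean ratio 0.95 to 1.02).

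Two runs added a quantification limit, at 20% residual error. Where the limit left Week 6 AUCtau evaluable in 21% of profiles (median 3 h) and 37% (median 6 h), 7% and 29% of Day 1 half-lives were left out. The geometric means moved from 3.1 to 2.9 h and from 6.3 to 6.0 h. Excluded values then started at 3.9 h and 3.2 h, while kept values ran to 13.4 h and 14.7 h, so the cut at the top was no longer clean.

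**Group size.** One withheld value is 1/8 = 12.5% of the Part 1 active sub-study group, or 1/6 = 16.7% of a Part 2 dose group.

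**The case against.** A reader might infer that valid clearances are lost and long half-lives deleted. The documents do not support that. Dose is fixed within a group and AUCtau is outside the slope test, so each withheld CLss/F is recoverable as Dose/AUCtau. Half-lives over 30% are listed with a flag, and the summaries show the number of observations.

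A reader might also infer a large downward bias. The rows from 10 to 20 h produce that, but no document gives such half-lives, and the protocol's statement of fast clearance points the other way. At 3 to 6 h with all samples quantifiable, 0% to 2% are left out. Nor does a long half-life always mean large extrapolation: if a terminal phase with a 20 h half-life carries 10% of total AUC, the share beyond 24 h is 0.10 × 0.5^(24/20) = 4.4%; at 50% it is 22%. Both would be kept. Saturable, target-mediated clearance makes a departure from mono-exponential decay plausible.

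Two further points stand. If the 24 h steady-state sample is unquantifiable, AUCtau may itself need the terminal slope, and a fit test on CLss/F is then defensible. Extrapolation above 30% also means, under mono-exponential decay, that sampling covered less than 1.204/0.693 = 1.74 half-lives, so the estimate is less precise. That would support a precision criterion, but it is not the reason the SAP gives, and Week 6, with the same 24 h span, has no such rule.

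Finally, no specified decision uses these parameters. The Part 2 dose criteria use AUC0-24hr and Cmax; exposure-response uses AUCtau, Cmax and Ctau.

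**Conclusion.** Both contradictions are in the SAP's own text and need no outside assumption. Their reach is limited. The first can put CLss/F and AUCtau summaries on different patients. The second tends to remove longer half-lives from the Day 1 summaries only.

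The size is uncertain. It runs from negligible for short half-lives with quantifiable 24 h samples to substantial if half-lives are long or the 24 h sample is often unquantifiable. The 13.8 h and 4.6 h cuts rest on mono-exponential decay. The simulated percentages rest on the assumed model, CV and error. With multi-phasic profiles the loss of long half-lives is only a tendency. This is a correction to a descriptive secondary-endpoint summary, worth making because it is cheap and the groups are small.

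**What to change.** Make two edits to SAP 8.7.4.3.

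1. Take CLss/F off the list governed by the terminal-slope criteria. Report it whenever AUCtau is evaluable under 8.7.4.2, and apply the slope criteria only where AUCtau itself needed terminal-slope extrapolation to reach 24 h.
2. Take t1/2 out of the 30% exclusion. Summarise every half-life that meets the three slope criteria, keep the flag for extrapolation above 30%, and add a sensitivity summary without the flagged values.

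Keep the 30% exclusion for AUC0-inf, CL/F, Vz/F and LR, which do contain AUC0-inf, and leave Vss/F under the slope criteria.

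The cost is two wording changes and one extra summary, with no new data. The drawback is that the Day 1 half-life summary will include some less precisely estimated values, which the flag and the sensitivity summary make visible.

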#### **8.7.5. Statistical Methods for Pharmacokinetic Parameters**

Plasma PK parameters will be summarized by treatment group using descriptive statistics (number of non-missing observations, arithmetic mean, SD, median, Q1, Q3, minimum, maximum, geometric mean, and geometric CV%).

For the calculation of summary statistics, all NR and not calculated (NC) values in a data series will be set to missing.

#### **8.7.6. Urine Pharmacokinetic Parameters**

[Table 7](#) presents the urine TERN-201 and its metabolites (TRN-001021 and TRN-001744) PK parameters to be calculated.

**Table 7: Urine Pharmacokinetic Parameters**

Abbreviation	Parameter Definition
CL R	Renal clearance, calculated over 0-8 h interval by dividing Ae 0-8h by AUC 0-8h , where the 0-8 h interval used is the same for Ae and AUC.
Ae	Amount of drug recovered from urine, amount will be calculated by multiplying urine concentration by urine volume. If the amount of urine is collected as weight rather than volume, Ae will be calculated by assuming a urine density of 1.0 g/mL.
fe	Percentage of dose recovered from urine, percentages will be calculated as Ae/dose × 100.

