MAD	Multiple ascending dose
MCH	Mean corpuscular hemoglobin
MCHC	Mean corpuscular hemoglobin concentration
MCV	Mean corpuscular volume
MedDRA	Medical Dictionary for Regulatory Activities
MMRM	Mixed model for repeated measures
MRI	Magnetic Resonance Imaging
MRI-PDFF	Magnetic Resonance Imaging Proton Density Fat Fraction
mRNA	Messenger RNA
MTD	Maximum tolerated dose
NAFLD	Nonalcoholic fatty liver disease
NASH	Nonalcoholic Steatohepatitis
NCI	National Cancer Institute
NFS	NAFLD fibrosis score
NIMP	Noninvestigational medicinal product
NOAEL	No observed adverse effect level
PCR	Polymerase chain reaction
PD	Pharmacodynamic(s)
PIIINP	Procollagen III N-terminal propeptide
PK	Pharmacokinetic(s)
po	Per os (oral)
PP	Per protocol
PPV	Positive predictive value
PRO-C3	Pro-peptide of type III collagen
PT	Prothrombin time
PTZ	Pentylenetetrazole
QD	Once daily
RBC	Red blood cell
RNA	Ribonucleic acid
SAD	Single ascending dose
SAE	Serious adverse event

Abbreviation or special term	Explanation
SAP	Statistical analysis plan
SARS-COV-2	Severe Acute Respiratory Syndrome Coronavirus 2
SCr	Standardized serum creatinine
SSAO	Semicarbazide-sensitive amine oxidase
SUSAR	Suspected unexpected serious adverse reactions
TEAE	Treatment emergent adverse event
TERN-201	An investigational selective VAP-1/SSAO inhibitor; a.k.a., LSN3415221 (LSN3379274·TsOH), LSN3394258 (LSN3379274·2HCl) and LSN3379274 (free base))
THC	Tetrahydrocannabinol
TIMP-1	Tissue inhibitor of metalloproteinases-1
TRN-001021	O-demethylation metabolite of TERN-201
TRN-001744	O-dealkylation metabolite of TERN-201
UACR	Urine albumin:creatinine
ULN	Upper limit of normal
UPCR	Urine protein: creatinine
US	United States
VAP-1	Vascular Adhesion Protein-1
VCAM-1	Vascular cell adhesion molecule-1
VLDL	Very low-density lipoprotein
WBC	White blood cell
WOCBP	Women of childbearing potential

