**Table 2: Study Administration by Dose Group**

Dose Group	TERN-201 Capsules	Placebo-to-Match
Part 1 – 10 mg	One 10 mg capsule QD	One placebo capsule QD
Part 2 – 4 mg	One 1 mg capsule and one 3 mg capsule QD	Two placebo capsules QD
Part 2 – 20 mg	Two 10 mg capsules QD	Two placebo capsules QD

**Abbreviations:** QD = once per day

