## **8.7. Pharmacokinetic (PK) Analyses**

Analyses of trough PK concentrations will use the PK Analysis Set. Analyses of intensive PK concentrations and PK parameters will use the PK/PD Substudy Analysis Set. All PK endpoints, recorded and derived, will be presented in by-patient data listings.

Plasma and urine TERN-201 and metabolite (TRN-001021 and TRN-001744) concentrations will be used as supplied by the analytical laboratory for PK analysis. The units of concentration and resulting PK parameters, with amount or concentration in the unit, will be presented as they are received from the analytical laboratory, with the exception of metabolite to parent ratios which will be corrected for differences in molecular weight. Urine volume will be presented with urine concentrations. Urine collection dates and times from the EDC will be used for analyses, otherwise plasma collection dates and times from the central vendor will be used.

Blood and urine samples will be collected at the timepoints specified in Appendix 2 of the study protocol.

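### SAP Table 7 computes metabolite urinary recovery (fe) as metabolite amount over parent dose with no molecular-weight factor; under three unstated assumptions it is too low by 29.6% (TRN-001744) and 4.8% (TRN-001021) in relative terms

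*SAP*

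**What the plan says.** SAP 8.7.6 says that Table 7 "presents the urine TERN-201 and its metabolites (TRN-001021 and TRN-001744) PK parameters to be calculated". Table 7 therefore governs all three analytes.

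Table 7 defines Ae by stating that the "amount will be calculated by multiplying urine concentration by urine volume". It defines fe as "Percentage of dose recovered from urine, percentages will be calculated as Ae/dose" times 100. Neither row contains a molecular-weight term, and there is no separate rule for the metabolites.

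Elsewhere the SAP does treat molecular weight. Section 8.7 presents amounts and concentrations in the units received from the laboratory, "with the exception of metabolite to parent ratios which will be corrected for differences in molecular weight". Section 8.7.4, in the text after Table 6, names the ratios: AUCtau, Ctau and Cmax, all in plasma. It says the ratio is multiplied by a factor: "The correction factor for TRN-001021 ratios is 1.05 and the correction factor for TRN-001744 ratios is 1.42".

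The dose is given in milligrams of TERN-201, for example "One 10 mg capsule QD" in SAP Table 2.

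**The concern.** A percentage of dose excreted as a metabolite should compare moles with moles, or convert the metabolite mass to its parent equivalent first. Table 7 does neither. The SAP recognises the difference in molecular weight when it forms the plasma ratios and supplies the constants, yet its urine formula omits them.

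Urine PK parameters for the metabolites are a named exploratory endpoint (Protocol Section 3; SAP 2.3.3). Reported metabolite fe would be biased by a constant that more patients cannot average out. The constant differs between the two metabolites, so their relative size would be distorted too.

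**Working it through.** The documents state no fe value, so there is no planned figure to reproduce. The check is one of units.

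**Inputs**
- fe = 100 x Ae/dose, with Ae = concentration x volume (SAP Table 7), for parent and both metabolites (SAP 8.7.6).
- Correction factors (CF): 1.05 for TRN-001021 and 1.42 for TRN-001744 (SAP 8.7.4).
- Dose in mg of TERN-201 (SAP Table 2).
- Direction: Protocol Appendix 9 describes TRN-001021 as the "O-demethylation metabolite of TERN-201" and TRN-001744 as an O-dealkylation product. Both should be lighter than the parent, which fits factors above 1 that equal MW(parent)/MW(metabolite).

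**Formula**
- Molar recovery = (Ae/MW metabolite)/(dose/MW parent) = (Ae/dose) x CF.
- fe as written, divided by molar recovery = 1/CF.
- Relative understatement = 1 - 1/CF.

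**Results** (range allows for rounding of CF by ±0.005)

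| Metabolite | CF | 1/CF | Understatement | Range |
|---|---|---|---|---|
| TRN-001744 | 1.42 | 0.704 | 29.6% | 29.3% to 29.8% |
| TRN-001021 | 1.05 | 0.952 | 4.8% | 4.3% to 5.2% |

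**Illustration** (assumed amount): 1 mg of metabolite recovered after a 10 mg dose gives fe = 10.0% under Table 7 for either metabolite. The molar value is 10.0 x 1.42 = 14.2% for TRN-001744 and 10.0 x 1.05 = 10.5% for TRN-001021.

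**Between metabolites:** the two biases differ by a factor of 1.42/1.05 = 1.35, so a comparison of the two recoveries is off by that factor.

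**Not affected by the omission:** parent fe has parent in numerator and denominator. Renal clearance divides Ae by the AUC of the same analyte, so molecular weight cancels.

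**The case against.** **Section 8.7 may already cover fe.** Its sentence concerns how units are presented for parameters that carry an amount or a concentration. fe is a percentage, and metabolite Ae over parent dose could be read as a kind of metabolite-to-parent ratio. This does not rescue the formula. The text that implements the correction begins "In addition, the metabolite-to-parent ratios will be calculated for AUC" and lists three plasma parameters only, while Table 7 writes fe out in full without a factor. A programmer working from Table 7 would not apply one.

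**The size depends on facts that the documents do not give.** This stands. The urine unit is not stated; mass units are an inference from mg doses and the ng/mL exposure limit in Protocol 4.1. The factors are not defined as parent/metabolite ratios. Protocol Appendix 9 lists a TsOH form, a 2HCl form and the free base, and the SAP does not say which of them the labelled dose or the factors refer to. If urine were reported in molar units, the percentages above would not apply, although Table 7 would then need a conversion of the dose that it does not give.

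**The plasma side is not fully corrected either.** This also stands. Table 6 is stated for the metabolites too and includes CL/F and Vz/F from dose without a molecular-weight term. The SAP's correction covers the plasma ratios, not all plasma parameters.

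**The consequence is small.** Agreed. Intensive sampling involves about 8 TERN-201 patients in Part 1 and about 6 per dose level in Part 2 (SAP 2.2). The interim decisions in SAP 8.3 do not use metabolite fe. PK endpoints are listed by patient, so a constant could be applied later.

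**Two stronger readings are tempting.** A reader might infer that total urinary recovery summed over parent and metabolites would be wrong; the documents plan no such sum. A reader might also infer that fe could pass for complete recovery because its row omits the interval. Protocol Appendix 2 provides only a 0-8 hour urine collection, and the renal clearance row of Table 7 names that interval, so this is a matter of labelling.

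**Conclusion.** The point holds as a wrong stated rule for an exploratory parameter. Table 7 covers the metabolites with an explicit formula that omits the conversion, and the correction given elsewhere does not reach it.

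On the three assumptions (mass units in urine, factors equal to parent/metabolite molecular weight, dose in the same parent form as the factors), metabolite fe is 29.6% too low for TRN-001744 and 4.8% too low for TRN-001021. These are relative figures: a true 10% recovery as TRN-001744 would be reported as 10/1.42 = 7.0%, a shortfall of 3.0 percentage points. Treating either figure as an unconditional error would go beyond the documents.

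No primary or secondary endpoint depends on it. It is worth correcting because the correction is simple, not because it threatens a conclusion of the trial.

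**What to change.** 1. Confirm with the bioanalytical laboratory the urine concentration units, the definition of the 1.05 and 1.42 factors, and whether dose and factors refer to the same parent form (salt or free base).
2. In Table 7, keep fe = 100 x Ae/dose for TERN-201, and add for the metabolites fe = 100 x (Ae x factor)/dose, with factor 1.05 for TRN-001021 and 1.42 for TRN-001744. Computing fe in molar units is equivalent.
3. Optionally, label the parameter as 0-8 hour recovery.

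The cost is one confirmation, one line of SAP text and one multiplication in the program. No new data are needed and trial conduct does not change.
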